1.2 STUDY DESIGN

This open-label extension (OLE) study is being conducted to confirm the long-term safety, efficacy, and pharmacokinetics of zinpentraxin alfa in the treatment of eligible patients with IPF. Eligible patients from the Phase II Study PRM-151-202 who have received the open-label zinpentraxin alfa will be enrolled into Cohort A and patients who have completed the Phase III Study WA42293 will be enrolled into Cohort B. Additionally, patients who have discontinued treatment from or have completed Study WA42293 and do not want to receive open-label zinpentraxin alfa in this study, will be invited to enroll in survival follow-up Cohort C. Patients in Cohort C will not receive any treatment and will not undergo any safety or efficacy assessments during the study (see [Figure 1](#)). Patients who discontinue treatment from Cohorts A and B will automatically transition to Cohort C for long-term follow-up, unless they withdraw consent from the study.

[figure not shown]
The study schema is shown in [Figure 2](#).

Figure 1 Cohort Allocation

^a Only Cohorts A and B receive active treatment.
OLE = open-label extension.

Figure 2 Study Schema

IV=intravenous; Q4W=every 4 weeks.
PRM-151 to be read as zinpentraxin alfa or rhPTX-2.

Patients meeting the eligibility criteria for the study will receive zinpentraxin alfa 10 mg/kg every 4 weeks (Q4W). Throughout the study, patients will be monitored for safety by collection of adverse events (AEs; both serious and non-serious) and by regular physical exam and safety laboratory assessments.

Efficacy will be evaluated through assessment of functional capacity as measured by forced vital capacity (FVC), 6-minute walk distance (6MWD), other pulmonary function tests (PFTs), and assessment of patients with respiratory events leading to hospitalizations, progression of disease, or acute IPF exacerbations.

Patient reported outcomes (PRO) will be assessed using the St. George Respiratory Questionnaire (SGRQ), University of California, San Diego Shortness of Breath Questionnaire (UCSD-SOBQ), and European Quality of Life Scale (EuroQol) 5-Dimension, 5-Level Questionnaire (EQ-5D-5L).

[figure not shown]
Dyspnea, fatigue, and blood oxygen saturation levels (SpO₂) will be assessed based on measurements taken during the 6-minute walk test (6MWT). High-resolution computed tomography (HRCT) of the chest will be assessed for changes between Week 52 from Study WA42293 to Week 52 (OLE) and Week 104 (OLE). Treated patients will be followed-up until the end of the study period, unless the patient withdraws consent for follow-up or death occurs.

For all patients receiving anti-fibrotic therapy, the investigator should document the dose, frequency, and duration of the anti-fibrotic drug.

During the study, patients may initiate background therapy of pirfenidone or nintedanib, if determined to be clinically indicated by the investigator. The study investigator is required to document the specific reason for introducing anti-fibrotic therapy in patients who started the study not on anti-fibrotic therapy.

Approximately 600–700 patients are expected to enroll in the study. Patients will initially receive loading doses of either zinpentraxin alfa 10 mg/kg intravenous (IV) infusion and/or placebo over 50–70 minutes on Days 1, 3, and 5, then one infusion of zinpentraxin alfa Q4W until the end of the study. Patients previously on the placebo arm of Study WA42293 will receive zinpentraxin alfa in all three loading doses, whereas patients previously on the active treatment arm of Study WA42293 will receive zinpentraxin alfa for the first dose, followed by placebo doses at the second and third loading dose visit. The loading doses will be blinded for Cohort B, to ensure that the blind in Study WA42293 is maintained for patients, site staff, and the Sponsor (see [Figure 3](#)).

Figure 3 Initial Loading Doses for Cohorts A and B

PRM-151 to be read as zinpentraxin alfa.

Patients entering Cohort A, from Study PRM-151-202, will have an eligibility visit prior to commencing dosing. The eligibility visit can occur on the same day as the dosing visit, if the patient is confirmed to be eligible for the study.

Patients entering Cohort B, from Study WA42293, will have their end-of-WA42293-study visit at Week 52. All assessments from the Week 52 Study WA42293 visit must be completed prior to commencing dosing in the OLE study. Ideally, patients will be enrolled into Cohort B on the same day as their Week 52 (Study WA42293) visit.

Patients enrolling into Cohort C from Study WA42293 (e.g., those who do not wish to receive study treatment), or those who transition from Cohorts A and B, will be followed-up for the duration of this study, to collect their survival data.

1.2.1 Treatment Assignment

In this study all patients in Cohorts A and B will receive zinpentraxin alfa.

Patients enrolling in Cohort A will receive three loading doses of open-label zinpentraxin alfa on Days 1, 3, and 5, followed by Q4W infusions.

For patients enrolling in Cohort B:

- Patients previously randomized to placebo in Study WA42293 will receive three loading doses on Days 1, 3, and 5 in a blinded fashion. All three doses will contain zinpentraxin alfa.

- Patients previously randomized to zinpentraxin alfa in Study WA42293 will receive three loading doses on Days 1, 3, and 5 in a blinded fashion. First of the three doses will contain zinpentraxin alfa, whereas the subsequent two doses will contain placebo.
- In order to maintain the blind to the treatment assignment of Study WA42293, all patients in Cohort B will be dosed in a blinded fashion on Days 1, 3, and 5 of the initial loading dose (see [Figure 3](#)).

If the first loading dose in patients in Cohort B is delayed and occurs more than 3 weeks (21 days) after the Week 52 visit in Study WA42293, patients will receive all three loading doses with zinpentraxin alfa (in a blinded fashion).

To minimize bias in this study, patients and the evaluating physicians will be blinded to treatment assignment of Study WA42293 until all patients have either completed the study or discontinued early from the study, the Study WA42293 database is locked, and the Study WA42293 analyses are final.

1.2.2 Independent Review Facility

An Anaphylaxis Adjudication Committee, an independent and blinded committee composed of external experts in allergic diseases, will adjudicate all potential anaphylaxis cases reported by investigators to the Sponsor. The committee will assess whether the reported event is a true anaphylaxis event (based on Sampson's criteria) and whether the reported anaphylaxis event is causally related to study treatment. Further details will be provided in the Anaphylaxis Adjudication Charter.

An independent, blinded Adjudication Committee will be convened to review all available data for all potential cases of acute exacerbations of IPF, hospitalizations for respiratory causes, and all deaths (applicable for Cohorts A and B only). This Adjudication Committee will be comprised of pulmonary disease physicians familiar with IPF exacerbations. A charter for the Adjudication Committee will provide further details. The Adjudication Committee will determine if the reported events meet the criteria of acute exacerbation of IPF, hospitalization for respiratory causes, and deaths (including deaths related specifically to respiratory causes) as defined in the charter.

1.2.2.1 Assessment for Suspected Anaphylaxis

Assessment of potential anaphylaxis will be conducted at every infusion per the clinical criterion for diagnosing anaphylaxis as described in Appendix 4 of Protocol – Sampson's Criteria for Diagnosing Potential Cases of Anaphylaxis. Patients experiencing suspected anaphylaxis should be managed as per local guidelines. Laboratory samples (serum tryptase, anti-drug antibody [ADA], complement C3) should be collected similarly to infusion-related reactions (IRRs).

All potential anaphylaxis cases reported by investigators to the Sponsor will be subsequently submitted for adjudication to an Anaphylaxis Adjudication Committee

composed of external experts in allergic diseases. The committee will assess whether the reported event is a true anaphylaxis event (based on Sampson's criteria) and whether the reported anaphylaxis event is causally related to zinpentraxin alfa.

If a patient has signs or symptoms of an anaphylactic or serious hypersensitivity reaction (including events deemed to have met the criteria as described by Sampson according to the blinded Anaphylaxis Adjudication Committee), administration of the study drug must be discontinued permanently.

Further details are outlined in the Anaphylaxis Adjudication Charter.

1.2.2.2 Acute Exacerbations of IPF and Suspected Acute Exacerbations of IPF

Acute exacerbation of IPF is defined as an acute, clinically significant respiratory deterioration characterized by evidence of new widespread alveolar abnormality, marked by the following diagnostic criteria ([Collard et al. 2016](#)):

- Previous or concurrent diagnosis of IPF
- Acute worsening or development of dyspnea typically <30 days in duration
- Computed tomography with new bilateral ground-glass opacity and/or consolidation superimposed on a background pattern consistent with usual interstitial pneumonia pattern
- Deterioration not fully explained by cardiac failure or fluid overload

Acute exacerbations of IPF are further categorized as triggered acute exacerbation or idiopathic acute exacerbation, depending on whether an underlying trigger for acute exacerbation is found (e.g., infection, post-procedural/postoperative, drug toxicity, aspiration).

Events that are clinically considered to meet the definition of acute exacerbation of IPF but fail to meet all four diagnostic criteria owing to missing computed tomography data are termed “suspected acute exacerbations of IPF”.

At each study visit, the investigator will ask directed questions and review the patient file to assess the possibility that the patient experienced an acute IPF exacerbation since the preceding study visit. An acute IPF exacerbation should be reported as an AE of special interest (see Section of the Protocol “Adverse Events of Special Interest [Immediately Reportable to the Sponsor]”) or serious adverse event (SAE) as applicable.

All relevant AE data (summary on clinical course, signs and symptoms; laboratory, lung function and imaging results; and treatment provided, including hospitalizations) relating to the exacerbation must be collected and entered onto the adverse event form. A charter for the Committee describes the process for the data to be reviewed and criteria for defining an IPF exacerbation.

1.2.2.3 Hospitalizations for Respiratory Causes

Hospitalizations for respiratory causes are defined as non-elective hospitalizations due to any respiratory cause, including acute exacerbations of IPF, or suspected acute exacerbations of IPF. All investigator-reported hospitalizations for respiratory causes will be assessed by an independent Adjudication Committee, as described in the charter.

1.2.2.4 Deaths due to Respiratory Causes

All deaths occurring during the study must be recorded. The event or condition that caused or contributed to the fatal outcome should be recorded as a single medical concept on the Adverse Event electronic Case Report Form (eCRF).

All investigator-reported deaths that occur in Cohorts A or B will be assessed by an independent Adjudication Committee to determine whether each death was related to IPF, another respiratory cause or an alternative (non-respiratory and non-IPF) cause. Deaths occurring in Cohort C will not be adjudicated.

1.2.2.5 Health Care Utilization for Respiratory Events

The following events will be recorded as health care utilization for respiratory events:

- Unscheduled visits to a healthcare professional/clinic for any respiratory event
- Urgent care or emergency room visits for respiratory events
- Hospitalization days for a respiratory cause, including for exacerbation of respiratory symptoms
- During hospitalization, any stay in ICU, including ICU days

1.2.3 Data Monitoring

An independent Data Monitoring Committee (iDMC) will be employed to monitor and evaluate patient safety in Study WA42294 only up until the time the database for primary analysis for Study WA42293 is locked and Study WA42293 is unblinded to the Sponsor (i.e., for the duration of Study WA42293), thereby better ensuring the safety of study patients. Consistent with U.S. Food and Drug Administration (FDA) recommendations ([FDA Guidance for Industry 2006](#)), the iDMC will be constituted of independent clinician experts in the field of IPF and clinical research and a statistician. A formal charter will be established for the conduct of the iDMC. The committee is planned to review the safety data in an unblinded manner.

2. STATISTICAL HYPOTHESES

Because of the non-comparative character of the study, no statistical tests are planned. All efficacy parameters will be summarized descriptively.

3. SAMPLE SIZE DETERMINATION

The number of patients enrolled in the OLE study is approximately 600-700 (i.e., eligible patients from Study PRM-151-202 [Cohort A] and Study WA42293 [Cohorts B and C]). No formal sample size calculations were performed.

4. ANALYSIS SETS

The analysis populations presented in this section are based on patients enrolled during the global enrollment phase of the study and will not include the China extension patients, unless otherwise specified.

The analysis populations are defined in [Table 2](#).

Table 2 Analysis Populations

Cohort	Population	Definition
Cohort A	Full analysis set (FAS)	All enrolled patients who received at least one administration (full or partial dose) of study drug.
	Safety-evaluable	All enrolled patients who received at least one administration (full or partial dose) of study drug.
	PRO-evaluable	All enrolled patients who received at least one administration (full or partial dose) of study drug and have a baseline and at least 1 post-baseline assessment.
	PK-evaluable	All enrolled patients who received at least one administration (full or partial dose) of study drug and have at least one evaluable post-dose PK sample that is above the lower limit of quantification and with sufficient data to determine plasma concentrations of zinpentraxin alfa at specified timepoints, unless major protocol deviations or unavailability of information (e.g., exact blood sampling time) occurred which may interfere with PK evaluation.
	Immunogenicity-evaluable	All enrolled patients who received at least one administration (full or partial dose) of study drug and have at least one ADA assessment.
	Biomarker-evaluable	All enrolled patients who received at least one administration (full or partial dose) of study drug and have genetic data to enable assessment of MUC5B status.

Table 2 Analysis Populations (cont.)

Cohort	Population	Definition
Cohort B	FAS	All enrolled patients who received at least one administration (full or partial dose) of study drug. Patients will be grouped according to the treatment assignment as described in Section 5.1.1 Treatment/Patient Group Terminology by Cohort.
	Safety-evaluable	All patients enrolled in the OLE study who received at least one administration (full or partial dose) of zinpentraxin alfa. Patients will be grouped according to the treatment assignment as described in Section 5.1.1 Treatment/Patient Group Terminology by Cohort.
	PRO-evaluable	All enrolled patients who received at least one administration (full or partial dose) of study drug and have an OLE baseline and at least 1 post-baseline assessment.
	HRCT-evaluable	All enrolled patients who received at least one administration (full or partial dose) of study drug and have an OLE baseline and at least 1 post-baseline assessment.
	PK-evaluable	All enrolled patients who received at least one administration (full or partial dose) of study drug and have at least one evaluable post-dose PK sample that is above the lower limit of quantification and with sufficient data to determine plasma concentrations of zinpentraxin alfa at specified timepoints, unless major protocol deviations or unavailability of information (e.g., exact blood sampling time) occurred which may interfere with PK evaluation.
Cohort A, B, C	Survival population	All patients that entered the study

FAS = full analysis set; HRCT = high-resolution computed tomography; PRO = patient-reported outcomes; PK = pharmacokinetic.

5. STATISTICAL ANALYSES

Because of the non-comparative character of the study, no statistical tests are planned. All efficacy parameters will be summarized descriptively. Demographic and baseline characteristics such as age, sex, race/ethnicity, concomitant IPF medication use, comorbid illnesses, and pulmonary function will be summarized by use of descriptive statistics.

The following sections are applicable to Cohorts A and B of the study. Patients initially allocated to Cohort C will be used for survival follow-up only without any safety or efficacy assessments.

5.1 GENERAL CONSIDERATIONS

All analyses will be reported separated by cohort.

Patients who are rolling-over from Study WA42293 will not be required to repeat safety and efficacy assessment at Day 1 if the visit occurs within 4 weeks of Week 52: in these cases, assessments from Week 52 of Study WA42293 will be used as Day 1 assessments.

The safety analyses will be performed on the safety-evaluable population, unless otherwise specified. Safety will be assessed through descriptive summaries of exposure to zinpentraxin alfa study drug, AEs, and laboratory test results.

All efficacy analyses will be performed on the full analysis set (FAS) population, unless otherwise specified. Patients in Cohort B will be analyzed according to the treatment assigned at randomization by interactive voice/Web-based response system (IxRS) in the parent study.

Cohort B collected data will not be analyzed before unblinding of the code of the treatment received by the patient during the parent Study WA42293. The main analysis will take place at the time of unblinding and main analysis of the parent Study WA42293. If unblinding of the Study WA42293 will occur earlier than the 52-week visit of the last patient enrolled in Cohort B, additional efficacy analysis will be implemented at the time when all patients in Cohort B had their 52-week visit or withdrew from the study, whichever is earlier.

Additional safety update analyses maybe conducted as required by Health Authorities. The final analysis will take place after the last patient last visit (LPLV).

All outputs relevant to Cohort C will have a footnote specifying that most part of the patients has contributed also to Cohort A and Cohort B.

5.1.1 Treatment/Patient Group Terminology by Cohort

The terminology of treatment/patient groups for each cohort under each analysis population is defined below:

Cohort A

- zinpentraxin alfa: all data for all patients

Cohort B

- Placebo: all data for patients as assigned to placebo during analysis in the parent study (actual or planned, depending on the type of the analysis)

- Zinpentraxin alfa: all data for patients as assigned to zinpentraxin alfa during analysis in the parent study (actual or planned, depending on the type of the analysis)
- All patients

Survival population for Cohort C

- From Cohort A: survival data from patients that discontinued or died from Cohort A
- From Cohort B: survival data from patients that discontinued or died from Cohort B for the following treatments
 - Placebo: survival data for patients as assigned to placebo during analysis in the parent study (planned treatment)
 - Zinpentraxin alfa: survival data for patients as assigned to zinpentraxin alfa during analysis in the parent study (planned treatment)
 - All patients
- Directly from Study WA42293: survival data from patients that have discontinued from study treatment or have completed Study WA42293 and have not wanted to receive open-label zinpentraxin alfa.
 - Placebo: survival data for patients as assigned to placebo during analysis in the parent study (planned treatment)
 - Zinpentraxin alfa: survival data for patients as assigned to zinpentraxin alfa during analysis in the parent study (planned treatment)
 - All patients

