5.4.1 Time-to-Event Endpoints

The time-to-event secondary endpoints are listed below:

- Time to disease progression, defined as time to first occurrence of $\geq 10\%$ absolute decline in % predicted FVC, $\geq 15\%$ relative decline in 6MWD, or death
- Survival, as measured by all-cause mortality, IPF-related mortality and respiratory-related mortality

Descriptive statistics for the frequency of each type of event will be provided. The Kaplan-Meier plot, median time to event, and their 95% CIs.

Time-to-event will be measured in reference to Baseline Day 1 of OLE study through the end of study or the time of the data-cut, whichever occurs first. For time to disease progression and survival (as measured by all-cause mortality, IPF-related mortality and respiratory-related mortality), patients without an event will be censored at the last clinic assessment.

The strategy for the time-to-event endpoints is summarized below in [Table 4](#).

Table 4 Strategy for Addressing Intercurrent Events: Time-to-Event Endpoints

Endpoint	Intercurrent Events and Strategy
Time to disease progression, defined as time to first occurrence of $\geq 10\%$ absolute decline in % predicted FVC, $\geq 15\%$ relative decline in 6MWD, or death	Any patients who undergo lung transplantation will be censored at the date of the transplant (hypothetical strategy) Any patients who withdraw from treatment will be censored at the date of last disease progression assessment, i.e., % predicted FVC and 6MWD (hypothetical strategy)
Survival, as measured by all-cause mortality, IPF-related mortality and respiratory-related mortality	Any patients who undergo lung transplantation will be censored at the date of the transplantation (hypothetical strategy) Any patients who withdraw from treatment will be censored at the date of withdrawal (hypothetical strategy)

6MWD = 6-minute walk distance; FVC = forced vital capacity; IPF = idiopathic pulmonary fibrosis.

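### SAP 5.1.1 puts Cohort A and B patients who died without discontinuing into the Cohort C survival groups, which overstates mortality there; separately, Table 4 censors A/B survival at treatment withdrawal

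*SAP*

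**What the plan says.** - **Entry to Cohort C.** SAP 1.2: "Patients who discontinue treatment from Cohorts A and B will automatically transition to Cohort C for long-term follow-up", unless they withdraw consent. Protocol 3.1.1 and 8.2 agree. Other patients join directly from Study WA42293.
- **Cohort C survival groups.** SAP 5.1.1: "From Cohort A: survival data from patients that discontinued or died from Cohort A". The Cohort B group has the same wording, split by parent-study arm. A third group holds the direct entrants.
- **Survival population.** SAP Table 2 defines it across Cohorts A, B and C as "All patients that entered the study".
- **Planned output.** SAP 5.1: "All outputs relevant to Cohort C will have a footnote", stating that most of these patients also contributed to A and B.
- **Survival rules.** SAP 5.4.1: "Time-to-event will be measured in reference to Baseline Day 1 of OLE study". Patients without an event are censored at their last clinic assessment. The survival row of Table 4 adds: "Any patients who withdraw from treatment will be censored at the date of withdrawal (hypothetical strategy").
- **Scope.** SAP 5 introduces its analysis sections with "The following sections are applicable to Cohorts A and B of the study" and uses patients initially allocated to Cohort C for survival follow-up only.
- **Adjudication.** SAP 1.2.2.4 sends deaths in A and B to the committee, whereas "Deaths occurring in Cohort C will not be adjudicated".
- **Purpose.** Protocol 3.3.3 and 4.6.1 say that survival data continue to be collected after treatment stops.

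**The concern.** The groups in SAP 5.1.1 are meant to describe survival in the follow-up cohort. Adding patients who died without discontinuing brings in people who were never followed there, and brings them in because they died. Their counterparts who are alive on treatment stay out. Every added patient is a death, so the group looks sicker than the patients who transitioned. Even a plain count of deaths, which needs no time origin, is affected.

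The second issue is separate and concerns the survival analysis of Cohorts A and B themselves. All-cause mortality is a listed efficacy endpoint. For an A/B patient, stopping treatment is the moment at which Cohort C follow-up begins, so censoring at treatment withdrawal leaves out every death recorded after it.

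**Working it through.** **No figure to reproduce.** The plan derives no sample size, event count or Cohort C statistic.

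**Direction.** Let s be the share of the 5.1.1 group who died without discontinuing, and p the proportion dead among those who really transitioned. The proportion dead in the 5.1.1 group is s + (1 − s)p. This exceeds p whenever s > 0 and p < 1, with no assumption about hazards.

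**Inputs for an illustration of size**
- Death hazard l = ln 2 / median. Protocol 3.3.3 gives a median survival of 2 to 5 years, so l = 0.347 to 0.139 per year.
- Discontinuation hazard d = 0.10 to 0.30 per year. This is an assumption; the documents give none.
- Constant hazards, discontinuation independent of death, and the same death hazard before and after stopping (assumptions).
- Cut at T = 2 years.

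**Formulas**
- Discontinued or died by T: q = 1 − exp(−(l + d)T)
- Share who died without discontinuing: s = l/(l + d)
- All deaths by T: D = 1 − exp(−lT)
- Proportion dead, 5.1.1 group: D/q
- Proportion dead, transitioned: (D − qs) / (q(1 − s))

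**One case in full** (l = 0.347, d = 0.10): q = 0.591, s = 0.776, D = 0.500. The 5.1.1 group has 0.500/0.591 = 0.847 dead. Deaths without discontinuation are qs = 0.458, and 0.132 transitioned, so 0.042/0.132 = 0.315 of those are dead. The ratio is 2.7.

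| Median (y) | d per year | s | Dead, 5.1.1 group | Dead, transitioned | Ratio |
|---|---|---|---|---|---|
| 2 | 0.10 | 0.776 | 0.847 | 0.315 | 2.7 |
| 2 | 0.20 | 0.634 | 0.752 | 0.322 | 2.3 |
| 2 | 0.30 | 0.536 | 0.689 | 0.330 | 2.1 |
| 5 | 0.10 | 0.581 | 0.638 | 0.136 | 4.7 |
| 5 | 0.20 | 0.409 | 0.492 | 0.140 | 3.5 |
| 5 | 0.30 | 0.316 | 0.415 | 0.144 | 2.9 |

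At a 5-year cut the ratio is 1.2 to 2.2.

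**If the hazard rises after stopping.** With a post-stopping hazard of k times l, deaths after transition become the integral over u from 0 to T of d·exp(−(l + d)u)·(1 − exp(−k·l·(T − u))). With k = 4 (an assumption), the ratio falls to 1.2 to 1.8 at 2 years and 1.02 to 1.21 at 5 years. The direction is unchanged.

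**Deaths removed by Table 4 in the A/B analysis.** With equal hazards, post-transition deaths by year 2 are D − qs, or 2 to 11 per 100 patients entering A or B. As a share of all deaths (D = 0.242 or 0.500), this runs from 0.042/0.500 = 8% to 0.058/0.242 = 24%.

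**The case against.** **The size rests on assumptions.** Protocol 4.6.1 lists safety-threatening medical conditions, serious reactions and transplant among the reasons for stopping, so independence and equal hazards are doubtful. The share is not bounded either: a death hazard of 0.05 with discontinuation of 0.30 gives 0.05/0.35 = 14%, below every row of the table. This stands. The figures illustrate; they are not limits.

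**The boundary is blurred.** Protocol Appendix 2 also lets patients enter survival follow-up after the last dose, and any death between infusions follows a last dose. But that footnote goes on to six-monthly contact, which presupposes a living patient, and SAP 1.2 names discontinuation as the route.

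**Table 2 and the footnote may cover it.** A population of all entrants can coexist with display groups inside it, so Table 2 is not in conflict. The footnote discloses overlap between cohorts but not selection on death, so neither repairs the definition.

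**Table 4 may be a deliberate estimand.** It is labelled hypothetical. It could stand as one analysis, but the SAP gives no companion that uses the deaths collected after stopping.

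**A stronger reading does not hold.** A reader might infer that 5.4.1 imposes an unworkable origin and censoring rule on Cohort C. The scope sentence in SAP 5 limits those sections to A and B, so what is documented for Cohort C is a gap, not a wrong rule. Nor do direct entrants lack any baseline: SAP 5.6.2 sets theirs at the first dose of the parent study, though for demographic and baseline summaries only. Mixing adjudicated and unadjudicated deaths also matters little, because no cause-specific Cohort C analysis is specified.

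**Conclusion.** The definition in SAP 5.1.1 is wrong as written. It selects on death and overstates mortality in the A- and B-derived Cohort C groups. That direction follows from the definition alone. The size cannot be known from the documents: under the stated assumptions it is 2.1 to 4.7 times at a 2-year cut, shrinking with longer follow-up or a higher hazard after stopping.

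Table 4 is a separate defect in the A/B survival analysis: its censoring at treatment withdrawal discards the deaths that continued survival follow-up is meant to capture.

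The consequence is limited to descriptive survival outputs. The full analysis set groups of Cohorts A and B do not carry the 5.1.1 selection, and no test or sample size depends on either point. A correction is still worth making, because in a study without tests the descriptive estimates are the result.

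**What to change.** 1. In SAP 5.1.1, remove the words *or died* from the A- and B-derived groups. Define them as patients alive at discontinuation, with time zero at transition to Cohort C.
2. Report all-cause survival for all patients entering Cohort A or B from OLE Day 1, including follow-up after transition. State that Table 4's censoring at treatment withdrawal does not apply to this analysis.
3. In both, censor survivors at the last date known alive. SAP 5.5.1 already uses that concept, and Cohort C contact is remote (Protocol 5.3.4 and Appendix 2), so there is no clinic assessment to censor at.
4. As a clarification only, state the survival origin for direct entrants: Cohort C enrolment or, if the parent-study Day 1 baseline of SAP 5.6.2 is used, delayed entry at enrolment so that the time before enrolment is not counted as time at risk.

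The cost is SAP wording and two derived dates (start of Cohort C follow-up and last date known alive). No new data collection is needed.
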